3 STUDY DESIGN AND DESCRIPTION

3.1 Study design

This is a prospective, randomized, multicenter, controlled, open, parallel group phase III study.

After initiation of the study, patients will be screened consecutively and eligible patients will be enrolled into the study at each center. To achieve comparable intervention groups and to minimize a potential selection bias, patients will be allocated in a concealed fashion by means of randomization using a centralized web-based tool (www.randomizer.at).

Each sites' principal investigator has to declare to the coordinating investigator/sponsor that he/she will conduct the study according to the protocol, ethical rules, and to provide the support as needed. To minimize a potential performance bias, this will be fixed in a contract prior to commencing the study. The clinical monitor will introduce the sites in detail to study procedures and documentation in advance.

Bias by potential influential factors will be addressed by inclusion as covariates into the statistical analysis. Independent clinical on-site monitoring to ensure patients safety and integrity of the clinical data in adherence to study protocol will focus on source data documentation, correctness of data, and adherence to study procedures, e.g. randomization and treatment.

Based on the performed interventions and planned analysis blinding is not feasible to minimize a detection bias, because the interventions can easily be differentiated due to visible side effects such as obesity, which is only expected in the control group. Furthermore, MMF is used in liquid form and prednisone as a tablet. The primary endpoint is based on standardized diagnostic work-up results, i.e. is an objective criteria.

3.2 Study Duration and Schedule

The duration of the study for each subject is expected to be 27 months (including 24 months follow-up after intervention)

Study duration:

Total study duration: [78 months] Duration of clinical phase: [63 months] Beginning of the preparation phase: [03/2014] FSI (first subject in): [01/2015] LSI (last subject in): [01/2018] LSO (last subject out): [04/2020] DBL (database lock): [07/2020] Statistical analyses completed: [08/2020] Study report completed: [04/2021]

4 SELECTION OF SUBJECTS

4.1 Number of Subjects

As calculated in section 8.1 Sample Size Calculation, 400 patients should be assessed for eligibility, 340 subjects should be enrolled in the clinical study, i.e. 170 subjects per treatment group. Recruitment and treatment of subjects should be performed in multiple study centers.

The study will be conducted on a multicenter basis. The rarity of the disease implicates a nationwide recruitment. The planned app. 45 study centers will be evenly distributed over Germany.

4.2 Inclusion Criteria

Subjects meeting all of the following criteria will be considered for admission to the study:

- First episode of steroid-sensitive nephrotic syndrome (SSNS)
- In remission induced by daily glucocorticoids within 28 days
- Male and female children aged ≥ 1 year and ≤ 10 years at beginning of study (typical age range of patients with SSNS)
- Ability of the persons having care and custody of the child to understand character and individual consequences of clinical study
- Written informed consent of the persons having care and custody of the child (must be available before enrolment in the study)

4.3 Exclusion Criteria

Subjects presenting with any of the following criteria will not be included in the study:

- Secondary nephrotic syndrome
- estimated glomerular filtration rate (eGFR) <90 ml/min x 1.73 m² BSA¹
- Ongoing treatment with systematically administered glucocorticoids or other immunosuppressive drugs at time of first episode of nephrotic syndrome.
- Hemoglobin concentration of ≤9 g/dL
- Leucocyte count of ≤2.500/µl
- Severe chronic gastrointestinal disease
- History of hypersensitivity to mycophenolate mofetil or to any drug with similar chemical structure or to any excipient present in the pharmaceutical form of suspension of mycophenolate mofetil (CellCept suspension®)
- Refusal of subject (please see also chapter 10.5)

Formula = (K * height [cm])/serum creatinine [mg/dl]

K = constant (determined by regression analysis) depends on the method of creatinine measurement:

- Jaffé method (photometric, kinetic measurement with picric acid) constant for age 1-13 years: K = 0.55 (Schwartz et al., 1976)
- Enzymatic measurement constant K = 0.413 (Schwartz et al., 2009)

¹ Estimated glomerular filtration rate

 Participation in other clinical studies or observation period of competing studies, respectively.

No subject will be allowed to enroll in this study more than once.

4.4 Withdrawal/premature closure

4.4.1 Withdrawal of Patients

a. Any patient can withdraw from treatment and/or from 24 months lasting follow-up at any time without personal disadvantages and without having to give any reason.

- Patients who discontinue treatment temporarily or completely (control intervention or experimental intervention) should be followed up until the end of study. The time and reason of treatment discontinuation must be documented in the patient file and in the eCRF.
- In patients, who discontinue participation in the INTENT-study, visit 8 (final visit) should be tried to be performed. The time and reason of study discontinuation must be documented in the patient file and in the eCRF. Patients who discontinue participation in the INTENT-study should be routinely treated by a physician or a pediatric nephrologist inside the study center or outside in an institution not taking part in the INTENT study. If the persons having care and custody of the child agree, routinely recorded data (e.g. relapse and treatment of relapse, serious adverse events (see 7.2), treatment with immunosuppressive drugs) may be used for the INTENT study. A separate informed consent form is available for this case (see separate informed consent form).
- b. The investigator may withdraw a patient from the treatment because of adverse events. These patients should be followed up until the end of study. In case of discontinuing mycophenolate mofetil (experimental intervention), the patient should be given the standard treatment (see control intervention). The time and reason of treatment discontinuation must be documented in the patient file and in the eCRF.

4.4.2 Premature Closure of the Clinical Study or a Site

If new information on the risk-to-benefit ratio of the drug or on the treatment methods used in the study is obtained in the meantime and safety concerns arise, the sponsor reserves the right to interrupt or terminate the project. Premature termination is also possible if the sponsor notices and agrees upon that patient recruitment is insufficient and that this cannot be expedited by appropriate measures.

Premature termination of a single center is also possible if the sponsor notices that the conduction of the study is not compliant with ICH-GCP and/or is not according to the protocol, the patient recruitment and/or the quality of the data is insufficient.

The DMSB can recommend interruption or termination of the study or of treatment arms based on the results of the intermittent SAE evaluation or of accumulating information on the above mentioned reasons.

The ethics committee (EC) and the competent authorities must be informed about the premature closure of the study or one of the treatment arms within 15 days by the sponsor. Furthermore, the ethics committee(s) and competent authorities themselves may decide to stop or suspend the study.

All involved investigators have to be informed immediately about a cessation/suspension of the study. The decision is binding to all study centers and investigators.

When the study is closed, all study materials (study medication etc.) must be sent to the sponsor.

5 INVESTIGATIONAL MEDICINAL PRODUCT (IMP)

5.1 Study medication

5.1.1 General Information

The sponsor will provide the quantity of study medication required for the clinical study. The medication provided must be used only in the context of this clinical study. Careful records will be kept of the study medication supplied to the centers and distributed to the patients. At the end of the study, all unused medication will be returned to sponsor. If deficiencies of the study medication are noticed, the monitor and project manager must be informed immediately.

5.1.2 Characterization of study medication

1. Mycophenolate mofetil

Proprietary name:	CellCept suspension®
International Nonproprietary Name (INN):	Mycophenolate mofetil (MMF)
ATC code, if officially registered:	L04AA06
Manufacturer:	Roche Registration Ltd.
Pharmaceutical formulation:	MMF is administered in liquid form (CellCept suspension® (Roche Registration Ltd.))
Mode of administration:	orally
Storage instructions:	The suspension expires 2 months after its assembly
	Storage of suspension below 30°C

2. Prednisone

Prednisone is used as standard therapy because it was used in the former studies of the GPN (standard treatment).

Proprietary name:	Decortin® (Merck Serono), Prednison GALEN®, (Galenpharma), Prednison acis® (Acis), Prednison Hexal® (Hexal), Prednison ratiopharm® (Ratiopharm), Cutason® (Mibe), Predni Tablinen® (Zentiva)	
International Nonproprietary Name (INN):	Prednisone	
ATC code, if officially registered:	H02AB07	
Manufacturer:	Merck Serono, Galenpharma, Acis, Hexal, Ratiopharm, Mibe, Zentiva	
Pharmaceutical formulation:	tablet	
Mode of administration:	orally	
Storage instructions:	Storage of below 25°C	

Note: Due to its pharmacokinetic characteristics prednisolone is not equal prednisone. The systemic availability of prednisolone after oral administration is 99%. The systemic availability of prednisone after oral administration differs between 62-99% in different publications (median: 79%) [22]. Some hospitals do not stock prednisone anymore, but only prednisolone. In case of admission of a study patient to these hospitals, prednisolone can be administered in a dose of 80% of the corresponding prednisone dose.

5.2 Packaging and Labelling

The study medication will be packed by the "Herstellbetrieb der Apotheke" of University Hospital Heidelberg. The study medication will be labeled and sent to the study sites by this pharmacy according to § 5 of GCP-V. The amount of medication per patient will be calculated according to body surface area and treatment strategy (both see 5.4) in the time period from day of randomization to end of intervention. The applicated amount of medication will be documented in the CRF.

5.3 Supplies and Drug Accountability

The investigator will confirm correct receipt of the study medication in writing and ensure that the medication is stored safely and correctly. The study medication must be carefully stored in accordance with manufacturer's instructions at room temperature and dry at the study sites and at the patient's home, in a locked area with restricted access, separately from other drugs, and kept out of the reach and sight of children. The investigator will document the distribution to and return of the study medication from the patient with the date, recording the quantity distributed and used on the forms provided for this purpose. The site monitor will periodically check the supplies of study medication held by the investigator to ensure the correct accountability of all study medication used. At the end of the study, all unused study medication and all medication containers will be completely disposed by the study centers. It will be assured that a final report of the drug accountability is prepared and maintained by the investigator.

5.4 Administration of study medication

5.4.1 Assignment of Identification Codes

For allocation to a treatment arm (randomization) see 5.5

Medication will be only provided to patients included into the study after randomization. The distribution of the medication will take place according to randomization.

5.4.2 Dosage Schedule

Maximum duration of treatment: 12 weeks after first day of initial treatment of SSNS. Patients will receive the whole medication for the complete intervention period.

Control intervention:

- The Prednisone, which is continued for a total of 6 weeks with the dosage of 60 mg/m² BSA/d (maximum 80 mg), is given once a day (quaque die (QD)), twice a day (bis in die (BID)) or three times daily (ter in die (TID)).
- The Prednisone, which is given for another total of 6 weeks with the dosage of 40 mg/m² BSA (maximum 60 mg) is given on alternate days (every other day) in one dose in the morning

Resorption of prednisone is independent of food intake.

Experimental intervention:

- Mycophenolate mofetil (MMF) is given in a dosage of 1200 mg/m² BSA/d as a suspension (200 mg/mL) until 12 weeks total treatment duration. MMF is given twice a day (bis in die (BID) = every 12 hours (± one hour).
- The suspension of MMF should be mixed in the study center (according to the Fachinformation).
- The persons having care and custody of the child are informed, that MMF should be given 30 minutes before or 60 minutes after food intake.
- For the first two weeks from randomization/visit1 on, prednisone is given with the dosage of 40 mg/m² BSA (maximum 60 mg) on alternate days (every other day) in one dose in the morning

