1 INTRODUCTION

1.1 Scientific Background

Idiopathic nephrotic syndrome in childhood

Clinical course and epidemiology

Idiopathic nephrotic syndrome in childhood, defined as the combination of heavy proteinuria (>40 mg/m² body surface area (BSA) per h) and hypalbuminemia (<25 g/L), accompanied by edema and hyperlipidemia, is a rare, relapsing disease with an incidence of 1.8 per 100.000 children below 16 years of age in Germany (ESPED registry 2005-2006), resulting in an annual rate of 200-250 patients [1]. The classification according to the four following categories is important for the clinical diagnostics, treatment and prognosis of the nephrotic syndrome in childhood: etiology, age at onset, histology, response to glucocorticoids. The primary idiopathic nephrotic syndrome with a typical onset of age (1-10 years of age) should be differentiated from patients with secondary causes or patients with age of onset younger than one year (congenital and infantile forms) or elder than 10 years of age. Approximately 80% of the children with idiopathic nephrotic syndrome have minimal change disease in renal biopsy, approximately 7% focal segmental glomerulosclerosis. The most important prognostic factor is steroid-sensitivity occurring in over 90% of the patients.

Treatment

The treatment of the first episode implies two aspects: (i) induction of remission, (ii) sustainment of remission. The German Society for Pediatric Nephrology (GPN), formerly known as Arbeitsgemeinschaft für pädiatrische Nephrologie (APN), formed the foundation for the standard of care of children with the nephrotic syndrome [2-7]. Thus, the recent guideline for the initial treatment of the first episode of a nephrotic syndrome recommends in detail: 60 mg prednisone/m² BSA per day for 6 weeks followed by alternate day prednisone 40 mg/m² BSA for another 6 weeks [8]. In case of steroid-sensitivity remission usually occurs within 7-14 days of treatment; the over-all duration of initial prednisone treatment is 12 weeks in order to sustain remission. This regimen has a relapse rate of 51% within 24 months after initial prednisone therapy, and a rate of frequent relapsers of 29% is expected.

Side effects of treatment

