8.3 Analysis Populations

The primary analysis will be performed for both the per-protocol population (PP) and the intention-to-treat population (ITT). The PP population comprises all patients, who were treated according to the randomized treatment as outlined in the protocol without major protocol violations (e.g., reduction of study medication of >50% or interruption of study medication of >3 days, violation of in- or exclusion criteria). The ITT population will compromise all patients randomized into the study. In this set, every patient is analyzed according to the group randomized into.

Since there may be patients who withdraw from the study after the treatment period or within the treatment period but consent to the incorporation of routinely recorded data was given the inclusion of these patients into the ITT population will be decided case by case before database lock and defined when writing the SAP. As appropriate, a third population will be defined for analysis of the primary and important secondary endpoints. How to deal with these patients and their data in detail depends on the time point of withdrawal and the amount and reliability of the routinely collected data.

The safety set will comprise all patients who have received study medication at least once, and will allocate the patients to the treatment they actually received, regardless of randomization. Whether routinely collected data of patients who withdraw prematurely can be included herein depends on the reliability of the collected safety data.

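### Taken literally as a single hand-out, the MMF supply rule outlasts the 2-month life of the mixed suspension; the protocol should say when the suspension is mixed and dispensed

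*Protocol*

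**What the plan says.** Three sections of the protocol bear on supply. Section 5.4.2 (Dosage Schedule) gives a rule for both arms: "Patients will receive the whole medication for the complete intervention period". In the MMF part it adds: "The suspension of MMF should be mixed in the study center", with a reference to the German product information but no date or visit. Section 5.2 (Packaging and Labelling) calculates the amount per patient "in the time period from day of randomization to end of intervention". Section 5.1.2 limits the mixed product: "The suspension expires 2 months after its assembly".

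The length of the MMF course follows from other statements. Section 5.4.2 sets the end: "Maximum duration of treatment: 12 weeks after first day of initial treatment of SSNS". Section 6.1 places visit 1 at 0 to 5 days after remission and visit 2 at 4 weeks (± 5 days) after visit 1. Section 1.1 says that "remission usually occurs within 7-14 days of treatment", while section 6.1 allows remission from day 5 to day 28.

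Section 8.3 lists "interruption of study medication of >3 days" among its examples of major protocol violations, which remove a patient from the per-protocol (PP) population. Under section 8.4 the confirmatory analysis is done in both the PP and the intention-to-treat populations.

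**The concern.** The supply rule reads most naturally as one hand-out covering the whole course. It would add little to section 5.2 if it meant only that enough drug is supplied overall. Visit 1 is also where families are told how to handle, dose and store the medication, and the descriptions of visits 2 and 3 mention no mixing or dispensing. Because the center does the mixing, no passage lets a family prepare a later bottle at home.

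A site that took the wording at face value would face one of two outcomes for a child with the usual remission time. Either the child takes suspension past its stated expiry, with potency not assured, or MMF runs out before the end of treatment. A shortfall of more than 3 days could be classed as a major violation and take the child out of the PP population. Both outcomes arise only in the experimental arm, have a purely logistic cause, and touch an analysis set that is confirmatory in a non-inferiority trial. Section 8.1 allows only 10% for major protocol violations.

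**Working it through.** The protocol gives no MMF duration or expiry figure in days, so there is no stated figure to reproduce. The check compares course length with shelf life, assuming that all suspension is mixed at visit 1 and MMF starts that day.

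**Inputs.**
- End of treatment: 12 weeks × 7 = day 84, counted from the first day of prednisone (section 5.4.2).
- Usual remission: day 7 to 14 (section 1.1). Permitted range: day 5 to 28 (section 6.1).
- Lag from remission to visit 1: 0 to 5 days (section 6.1).
- Shelf life: 2 months (section 5.1.2). The length in days is an assumption; calendar months give 59 to 62.

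**Formulas.** Start day s = remission day + lag, so the usual child starts between day 7 + 0 = 7 and day 14 + 5 = 19. MMF days = 84 − s, or 85 − s if both end days are counted. Overrun = MMF days − shelf life.

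**Results** (each cell gives the two day counts; a negative value means the course fits):

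| Start day | MMF days | Overrun at 59 d | at 60 d | at 61 d | at 62 d |
|---|---|---|---|---|---|
| 5 (earliest) | 79 / 80 | 20 / 21 | 19 / 20 | 18 / 19 | 17 / 18 |
| 7 (usual, early) | 77 / 78 | 18 / 19 | 17 / 18 | 16 / 17 | 15 / 16 |
| 19 (usual, late) | 65 / 66 | 6 / 7 | 5 / 6 | 4 / 5 | 3 / 4 |
| 24 | 60 / 61 | 1 / 2 | 0 / 1 | −1 / 0 | −2 / −1 |
| 33 (latest) | 51 / 52 | −8 / −7 | −9 / −8 | −10 / −9 | −11 / −10 |

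For the usual child the course is 65 to 78 days. The overrun is 3 days at the least (65 − 62) and 19 at the most (78 − 59). It is 5 to 17 days with 60 days and the first count, and also with 61 days and the second count. On the latter basis, 17/78 = 22% of the course falls after expiry for a start on day 7, and 5/66 = 8% for a start on day 19.

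**Against the 3-day limit.** Across starts on day 7 to 19, the overrun exceeds 3 days in every combination but one: a start on day 19, 62-day months and the first count, which give exactly 3.

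**Would later mixing remove the conflict?** The earliest visit 2 is day 5 + 28 − 5 = day 28. From then to day 84 inclusive there are 85 − 28 = 57 days, below the shortest shelf life of 59. The latest visit 2 is 28 + 5 = 33 days after visit 1, so a first portion would not expire before it either.

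**The case against.** The strongest reply is that the protocol nowhere says the whole supply is mixed and handed out at visit 1. The supply rule names no visit, covers both arms, and can mean that the full amount is supplied over the period. Section 5.2 fixes how much is calculated, not when it is mixed. The 2 months run from assembly, so a center holding the full amount could mix part of it later and satisfy all three sections. Section 5.3 is compatible with this: it refers to stock held by the investigator, has distribution recorded with date and quantity, and requires storage according to the manufacturer's instructions. The silence of visits 2 and 3 on dispensing proves little, because the visit 1 description does not mention dispensing either.

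Most of this stands. A reader might infer that the supply rule and the shelf life cannot both be met, or that every usual MMF patient must either take expired drug or leave the PP population. The documents support neither inference. Later mixing is not forbidden, and the visit 2 dates show that both rules can be met together. Nor do the documents give the number of children affected, any loss of potency, or an effect on the PP comparison. It is also arguable whether running out early is an interruption in the sense of section 8.3, although its list is only illustrative and PP membership requires treatment as the protocol outlines.

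What the reply does not remove is that a stated supply rule, followed in its plain sense, breaches a stated shelf life at the usual remission time, and that no passage plans the later mixing that would avoid it.

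**Conclusion.** The point holds as a conditional inconsistency of moderate weight. If the suspension is mixed and handed out once at visit 1, a child with the usual remission time needs MMF for about 65 to 78 days from a product that lasts an assumed 59 to 62 days. The overrun is about 3 to 19 days, and about 5 to 17 at 60 to 61 days. Children who start on about day 24 or later fit.

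The size rests on three things: the one-time reading of section 5.4.2, the assumed length of 2 months, and the usual remission time, which is a background statement in section 1.1. No distribution of remission times is given, so the share of the MMF arm affected cannot be calculated.

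**What to change.** Reconcile sections 5.1.2, 5.2 and 5.4.2 by stating when the suspension is mixed and when it is dispensed, so that no portion is used beyond its stated expiry. On the protocol's own dates, mixing a later portion at the existing visit 2 would meet this condition. The sponsor may choose another arrangement that also meets it. Record the mixing date of each portion on the drug accountability form required by section 5.3.

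The change concerns supply only; dose and treatment duration are unchanged. It costs a short amendment, an instruction to the pharmacy and centers, and some part-used bottles. If visit 2 is used, no extra visit or procedure is needed.
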